### 2.3.3. Additional Estimands for Primary Endpoint

A supplementary (Estimand 4) estimand for the primary endpoint will use the hypothetical strategy, which estimates the treatment effect if all patients adhere to the protocol and the intercurrent event of investigational product discontinuation has not occurred. It differs from the primary estimand in the following 2 attributes:

- Variable: time to sJIA disease flare in the double-blind phase.

Patients who discontinue from investigational product for reasons other than flare in the double-blind phase and who complete study participation after achieving clinical remission, will be considered as non-flare and censored at the last available flare assessment while on investigational product. (More details of on-treatment censoring time and risk period are provided in [Section 5.3.1.1](#).)
- Intercurrent event: all data after an intercurrent event (investigational product discontinuation), if collected, will be excluded.

A second supplementary estimand (Estimand 5) for the primary endpoint will use the treatment policy strategy and estimate the treatment difference regardless of whether an intercurrent event occurs. It differs from the primary estimand in the following 2 attributes:

- Variable: time to sJIA disease flare in the double-blind phase.

- Intercurrent event: investigational product discontinuation is not considered for analysis. All the flare data collected both on-treatment and off-treatment in the double-blind phase of Study A3921165 will be used. For subjects who withdraw from study early, before reaching 52 weeks of double-blind treatment from Study A3921165 and enrolled in the LTE (Study A3921145), the flare data collected through Week 52 post randomization from both studies A3921165 and A3921145 will be included (see [Section 6.1.2.1](#)). (More details of on-study censoring time and risk period are provided in [Section 5.3.1.1](#).)

#### 2.3.4. Additional Estimands for Selected Secondary Endpoints

For aJIA ACR 30/50/70/90/100 response at each double-blind phase visit, a supplementary estimand (Estimand 6) will use the treatment policy strategy. It estimates the effect regardless of treatment adherence. It differs from the composite estimand ([Section 2.3.2.1](#)) in the following 2 attributes:

- Variable: aJIA ACR 30/50/70/90/100 response at each double-blind phase visit through Week 52.
- Intercurrent event: the intercurrent event of investigational product discontinuation will not be considered. More specifically, unlike Estimand 2, LOCF is not applicable and subjects who discontinue from investigational product will not be considered as ACR non-responders. All the aJIA ACR data collected while On- and Off-investigational product until Week 52 will be used to derive the endpoints.

For all secondary continuous endpoints in double-blind phase ([Section 3.2.1](#)), the estimand will use the hypothetical strategy (Estimand 7). It differs from the treatment policy estimand ([Section 2.3.2.2](#)) in the following 2 attributes:

- Variable: secondary continuous endpoints such as change from double-blind baseline in JADAS-27 CRP and JADAS-27 ESR at each scheduled visit through Week 52 in the double-blind phase.
- Intercurrent event: investigational product discontinuation will be the intercurrent event. All data after the intercurrent event, if collected, will be excluded; ie, only the on-treatment data ([Appendix 3.13](#)) will be used.

### 3. ENDPOINTS AND BASELINE VARIABLES: DEFINITIONS AND CONVENTIONS

#### 3.1. Primary Endpoint

- Time to sJIA disease flare in the double-blind randomized withdrawal phase.

Time to the disease flare event is defined as the number of days from randomization to flare in the double-blind phase and calculated as date of disease flare – date of randomization +1.

Details for the derivation of disease flare are described in [Appendix 3.3](#). Additional disease flares related to intercurrent events occurrence are differently defined for different estimands

in [Sections 2.3.1](#) and [2.3.3](#). Different imputation methods of disease flare dates for the censored data are described separately in [Sections 6.1.1](#), [6.1.2.1](#) and [6.1.2.2](#).

### **3.2. Secondary Efficacy Endpoints**

#### **3.2.1. Double-blind Randomized Withdrawal Phase**

- Occurrence of disease flares in the double-blind phase at each visit.
- Adapted JIA ACR 30/50/70/90/100 response at every visit in the double-blind phase, with individual component improvements calculated relative to the open-label baseline.
- “Absence of fever”, defined as absence of fever (fever defined as oral temperature  $>38^{\circ}\text{C}/100.4^{\circ}\text{F}$ ) due to sJIA in the week preceding the assessment at every visit in the double-blind phase.
- Change from DB baseline in Juvenile Arthritis Disease Activity Score (JADAS-27, calculated based on the ESR and CRP inflammation biomarkers separately) at every visit in the double-blind phase.
- Change from baseline (both open-label and double-blind baseline) in each sJIA ACR core variable (i.e., number of joints with active arthritis, number of joints with limited range of motion, physician global evaluation of disease activity, parent/legal guardian/subject evaluation of overall well-being (from the CHAQ), disability index from the CHAQ, and ESR) at every visit in the double-blind phase.
- Occurrence of inactive disease status and minimal disease activity (JADAS-27, calculated based on the ESR and CRP inflammation biomarkers separately) at every visit in the double-blind phase. Refer to [Appendix 3.6](#) for detailed definitions.
- Occurrence of JIA ACR inactive disease status at every visit in the double-blind phase. Refer to [Appendix 3.7](#) for detailed definitions.
- Clinical remission (24 weeks consecutive JIA ACR inactive disease, starting from double-blind phase day 1) in the double-blind phase.
- Change from DB baseline in Child Health Questionnaire (CHQ) responses every 6 months thereafter in the double-blind phase.
- Change from DB baseline in Child Health Assessment Questionnaire (CHAQ) - Discomfort Index at every visit in the double-blind phase.

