- If the value of the test-statistic at the First Analysis crosses the futility boundary ($z \geq -0.286$, 1-sided $p \geq 0.387$), the trial may be stopped for futility.
- Otherwise, the trial will continue as planned. The Final Analysis will be performed after flares have been reported in approximately 40 subjects.

The efficacy and futility boundaries will depend on the number of flares. For logistical and administrative reasons, the actual number of flares at the First Analysis and the Final Analysis might differ slightly from those that have been pre-specified here. In that case appropriate adjustments will be made to the efficacy and futility boundaries based on the gamma family spending functions. The actual boundary used for the First or the Final Analysis will be re-calculated from the specified spending function based on the actual number of flares achieved at the time of First or Final analysis. These boundaries will be calculated and finalized prior to the evaluation of comparative data. More details regarding the calculation of futility and efficacy boundaries will be provided in the SAP.

Applying a 1:1 allocation ratio to treatment groups and an Adapted JIA ACR response rate of approximately 55% at the end of the open-label phase, it is estimated that approximately 100 subjects would need to be enrolled in the open-label phase to randomize 54 subjects in the double-blind phase. As of November 2022, 23 subjects have been randomized during the accrual period of 225 weeks. Assuming a future accrual rate of 0.315 subjects per week, it is anticipated that it will take a total of 262 and 358 weeks to achieve the requisite number of flares for the First and Final Analyses, respectively.

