## **2.2. Study Design**

This is a 2-phase randomized withdrawal study to evaluate efficacy, safety and tolerability, and pharmacokinetics of tofacitinib as a treatment for sJIA. The study will enroll approximately 100 subjects from 2 to <18 years of age with sJIA with active systemic features.

The study will target enrollment of at least 12 subjects in the following age groups: from 12 to <18 years, from 6 <12 years, and from 2 to <6 years.

The study will conclude when the requisite number of flares are achieved during the double-blind phase of the study as described in [Section 5.1 Hypotheses and Decision Rules](#).

Subjects will be enrolled into an open-label phase during which they will receive tofacitinib 5 mg twice daily (BID) oral tablets, or an equivalent weight-based lower dose of tofacitinib oral solution (1 mg/mL) BID for subjects <40 kg. The 5 mg BID dose level of tofacitinib will be evaluated in a staggered fashion (cohorts of 7 subjects followed by safety review).

The open-label phase will be divided into two parts. In Part 1, all subjects must achieve and maintain a protocol-defined minimum level of clinical response for at least 4 weeks. In Part 2 of the open-label phase, subjects treated with background CSs >0.2 mg/kg/day oral prednisone (or equivalent) will attempt to have their CS dose tapered to a predetermined target range, or lower; subjects who successfully taper their CS dose while maintaining the defined clinical response, will be eligible for the double-blind withdrawal phase of the study. The minimum total duration of treatment with a stable dose of tofacitinib for subjects completing Parts 1 and 2 must be 12 weeks to qualify to enter the randomized withdrawal phase of the study.

In the double-blind withdrawal phase, “responders” from Part 1 and Part 2 of the open-label phase will be randomized in a 1:1 ratio, stratified by age group (from 12 to <18 years, from 6 <12 years, and from 2 to <6 years), to either continue tofacitinib or withdraw from tofacitinib and start placebo. The primary endpoint of the study is time to sJIA flare in the double-blind phase. The double-blind withdrawal phase will continue until a sufficient number of flares are reported as described in Section 5.1.

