## 4. ANALYSIS SETS

### 4.1. Double-Blind Analysis Sets

#### 4.1.1. Double-Blind Full Analysis Set

The Double-Blind Full Analysis Set (DBFAS) will consist of all randomized subjects who received at least one dose of investigational product in the double-blind phase. Subjects will be reported under the treatment they were randomized to. In this study, the primary efficacy analysis will be performed on the DBFAS. Secondary endpoints for the double-blind randomized withdrawal phase will also be analyzed using the DBFAS.

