### 5.2.2. Analyses for Binary Data

Open-label binary endpoints will be analyzed using the normal approximation to binomial proportion.

The normal approximation 95% CI is calculated as:

$$\hat{p} \pm z_{0.975} \sqrt{\frac{\hat{p}(1 - \hat{p})}{N}}$$

where  $\hat{p}$  is the estimated response rate,  $z_{0.975}$  is the 97.5th percentile of the standard normal distribution and N is the number of subjects evaluable for the endpoint at the time point. If the lower bound is calculated to be negative, it will be set to 0%; if the upper bound is calculated to be larger than 100%, it will be set to 100%. In case when response rate is 0 or 100%, standard error will be reported as "NA" and the 95% CI bounds will be the same as the response rate.

For the double-blind binary endpoint at a single time point (eg, adapted JIA ACR 30/50/70/90/100 response at each DB phase visit), the normal approximation for the difference in binomial proportions can be used to test the superiority of tofacitinib 5 mg BID to placebo at DB phase timepoints. The normal approximation to the test statistic for the difference in binomial random variables is calculated as

$$Z = \frac{\hat{p}_t - \hat{p}_c}{\sqrt{\frac{\hat{p}_t(1 - \hat{p}_t)}{N_t} + \frac{\hat{p}_c(1 - \hat{p}_c)}{N_c}}}$$

where  $\hat{p}$  refers to the relative frequency,  $N$  to the number of observations, the subscript  $c$  refers to the comparator group (e.g., placebo group) and the subscript  $t$  refers to the test group (e.g., tofacitinib 5 mg BID group) so that test statistics and p-values can be calculated for the contrast comparing the two treatment groups.

Two-sided 95% confidence intervals will be formed by

$$\hat{p}_t - \hat{p}_c \pm z_{0.975} \sqrt{\frac{\hat{p}_t(1 - \hat{p}_t)}{N_t} + \frac{\hat{p}_c(1 - \hat{p}_c)}{N_c}}$$

Two-sided p-value for the test of the 0 difference between tofacitinib 5 mg BID and placebo groups will be calculated as:

$$p = 2(1 - \Phi(|Z|)),$$

where  $\Phi(.)$  is the Gaussian cumulative density function.

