#### 6.2.1.1. Binary Secondary Endpoints in Double-Blind Phase

Except the endpoint of occurrence of disease flare by visit, which is estimated in the analyses of the primary endpoint (Section 6.1.1 and Section 6.1.2.1), all other DB binary secondary endpoints listed in Section 3.2.1 (aJIA ACR 30/50/70/90/100 response, absence of fever, occurrence of inactive disease and minimal disease activity, occurrence of JIA ACR inactive disease and clinical remission), are analyzed as below:

- Estimand strategy: Composite (Section 2.3.2.1).
- Analysis set: DBFAS (Section 4.1.1).
- Analysis methodology: Descriptive summary in Section 5.2 and analysis methods in Section 5.2.2 will be followed.
- Intercurrent events and missing data: See definitions described in Section 2.3.2.1 for intercurrent events and Section 5.3.2 for missing data.
- The basic summary statistics will be calculated by visit. The normal-approximated 95% CI and 2-sided p-value for the treatment effect will be presented at each scheduled visit in the double-blind phase through Week 52.

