**Table 4. Summary of Efficacy Analyses**

Endpoint	Estimand and Analysis Type	Population	Data Inclusion and Rules for Handling Intercurrent Events and Missing Data	Analysis Model
JADAS-27 CRP minimal disease activity by DB visit	Secondary estimand  Estimand 2 Composite Strategy  Secondary analysis	DBFAS	For investigational product discontinuation due to study end and end of study treatment after clinical remission, use last JADAS-27 CRP value before discontinuation.  Investigational product discontinuation for any other reason are treated as non-response for minimal disease activity.  Missing responses are treated as non-response for minimal disease activity.	Normal approximation
Absence of fever by DB visit	Secondary estimand  Estimand 2 Composite Strategy  Secondary analysis	DBFAS	For investigational product discontinuation due to study end and end of study treatment after clinical remission, use last oral temperature value before discontinuation.  Investigational product discontinuation for any other reason are treated as fever.  Missing responses are treated as fever.	Normal approximation
JIA ACR inactive disease by DB visit	Secondary estimand  Estimand 2 Composite Strategy  Secondary analysis	DBFAS	For investigational product discontinuation due to study end and end of study treatment after clinical remission, use last JIA ACR value before discontinuation.  Investigational product discontinuation for any other reason are treated as non-response.  Missing responses are treated as active disease.	Normal approximation
Clinical remission in DB phase	Secondary estimand	DBFAS	For investigational product discontinuation due to study end and end of study treatment after clinical remission, use last clinical	Normal approximation

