**Table 4. Summary of Efficacy Analyses**

Endpoint	Estimand and Analysis Type	Population	Data Inclusion and Rules for Handling Intercurrent Events and Missing Data	Analysis Model
	Estimand 2 Composite Strategy  Secondary analysis		remission status before discontinuation. Investigational product discontinuation for any other reason are treated as non-response for active disease.  Missing responses are treated as active disease.	
ACR 30/50/70 response and JIA ACR inactive disease by DB visit and by subgroups: age, body weight, geographic region, formulation, OL baseline oral corticosteroids use, DB baseline oral corticosteroid use, OL baseline MTX use, prior bDMARD experience	Secondary estimand  Estimand 2 Composite Strategy  Subset analysis	DBFAS	For investigational product discontinuation due to study end and end of study treatment after clinical remission, use last JIA ACR value before discontinuation. Investigational product discontinuation for any other reason are treated as non-response/active disease.  Missing responses are treated as non-response/active disease.	Normal approximation
JADAS-27 ESR scores change from DB baseline by DB visit	Estimand 7 Hypothetical Strategy  Secondary analysis	DBFAS	Only data collected On-investigational product are included.  Missing data are not imputed and handled using MMRM.	MMRM with terms treatment, visit, treatment*visit, DB baseline, DB baseline*visit
JADAS-27 CRP scores change from DB baseline by DB visit	Estimand 7 Hypothetical Strategy  Secondary analysis	DBFAS	Only data collected On-investigational product are included.  Missing data are not imputed and handled using MMRM.	MMRM with terms treatment, visit, treatment*visit, DB baseline, DB baseline*visit

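### If the trial stops at the First Analysis, children randomised less than 24 weeks before study end are scored as clinical remission failures for lack of time, so both rates and their absolute difference are understated in expectation

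*SAP*

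**What the plan says.** - **Endpoint.** SAP 3.2.1: "Clinical remission (24 weeks consecutive JIA ACR inactive disease, starting from double-blind phase day 1) in the double-blind phase". SAP 5.3.2.3 repeats that the 24 weeks are counted from double-blind Day 1.
- **Population.** The DBFAS (SAP 4.1.1) is "all randomized subjects who received at least one dose of investigational product in the double-blind phase". No minimum follow-up is required.
- **Method.** SAP 6.2.1.1 lists the endpoint among the composite-strategy binary outcomes: "occurrence of JIA ACR inactive disease and clinical remission), are analyzed as below". SAP 5.2.2 states that "the normal approximation for the difference in binomial proportions can be used to test the superiority of tofacitinib 5 mg BID to placebo".
- **Child stopped by study end.** The clinical remission row of SAP Table 4 reads "For investigational product discontinuation due to study end and end of study treatment after clinical remission, use last clinical" and continues, after a page break, "remission status before discontinuation. Investigational product discontinuation for any other reason are treated as non-response for active disease". SAP 5.3.2 sets any other missing response to non-response. SAP 5.3.2.3 exempts carried-forward cases from derivation out of inactive disease, so the status is not rebuilt.
- **Study end.** SAP 2.2: "The study will conclude when the requisite number of flares are achieved during the double-blind phase of the study". Protocol 3.3 and 6.8 then call all remaining children for an end-of-study visit.
- **The same child elsewhere.** For the primary endpoint, SAP 2.3.1 censors a child still active at study end. SAP 2.3.4 adds a treatment-policy supplement for the adapted JIA ACR responses, but none for remission.

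**The concern.** Remission cannot be reached before 24 weeks. The date on which follow-up stops is set by a flare count, and under the protocol's projection randomisation is still open when the 28th flare occurs. Some children in the denominator therefore never had the time to succeed, and the plan counts lack of time as treatment failure.

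The reported percentages would then estimate neither a 24-week nor a 52-week probability. They would depend on how many children happened to be randomised late. With 1:1 allocation both arms lose the same expected share, so the absolute difference shrinks by that share too.

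**Working it through.** **Inputs from the documents.** Protocol 10.1.1 gives 23 children randomised in 225 weeks, then "Assuming a future accrual rate of 0.315 subjects per week", up to 54. It also gives a hazard ratio of 0.36, a placebo median of 236 days and 1:1 allocation. SAP 5.1 gives 28 flares at the First Analysis and 37 at the Final Analysis. Weekly hazards are placebo ln 2 × 7/236 = 0.0206 and tofacitinib 0.36 × 0.0206 = 0.0074.

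**1. Reproduce the plan's calendar.** For entries at rate r between weeks a and b, the expected flares by week t are the sum over the two arms of (r/2) × [(b − a) − (e^(−λ(t−b)) − e^(−λ(t−a)))/λ]. This gives 20 flares at week 261.6 and 40 at week 358.3, against 262 and 358 in Protocol 10.1.1. The SAP design (28/37 flares, z −1.973 and −2.586, power 80.4%) also reproduces.

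**2. Affected share, no remission exits.** The formula puts 28 flares at week 300.9 and 37 at week 340.4. The 54th child enters at 225 + 31/0.315 = week 323.4.
- 28 flares: randomised 23 + 0.315 × 75.9 = 46.9. In the last 24 weeks 0.315 × 24 = 7.56, so 7.56/46.9 = 16%.
- 37 flares: entries between weeks 316.4 and 323.4 number 0.315 × 7.0 = 2.2, so 2.2/54 = 4%.

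A simulation of the event-driven stop gives 17% (5th–95th percentile 8–26%) and 6% (0–17%).

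**3. Allow for remission exits.** A child in remission completes the study and is not a flare (Protocol 3.3), so exits delay the flare count. The documents give no remission rates. The rates below are assumptions (tofacitinib versus placebo), with exit at Week 24.

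| Assumed remission | Share at 28 flares | Share at 37 flares |
|---|---|---|
| No exits | 17% | 6% |
| 30% vs 10% | 12% | 0.6% |
| 40% vs 15% | 8.6% | 0.2% |

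In the last row the 28th flare comes at about week 337. No child is affected in 26% of runs. About 20% of runs never reach 37 flares with 54 children.

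**4. Allow for a lag.** The documents give no interval between the deciding flare and study end. Assume 8 to 16 weeks, with no exits. If randomisation is paused at the trigger, the 17% falls to 11–5.5%. If it continues, the share is 15–13%. Exits and a paused lag together would lower it further.

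**5. Effect on the estimate.** Expected crude rate = (1 − share) × rate with full 24-week opportunity. At 40% versus 15% and a share of 8.6%: 40 × 0.914 = 36.6 and 15 × 0.914 = 13.7. The difference is 22.9 points rather than 25.

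**6. How likely is a First Analysis stop?** Under HR 0.36 the expected z at 28 flares is −(√28/2) × 1.022 = −2.70. The chance of z ≤ −1.973 is about 77%. Adding the futility boundary (z ≥ −1.240), about 84% of trials cross a boundary, where the rules allow a stop.

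**The case against.** The mechanism is not disputed, but its size and consequences can be read too strongly.

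- A reader might infer that the understatement is a general feature of the trial and amounts to 16–17%. The documents do not support that. Those figures assume no child leaves in remission, whereas Protocol 3.3 makes remission a route out of the study. Applying 16% to rates of 40% and 15% would cut 25 points to about 21, but that combines a no-exit calendar with rates that imply many exits. The consistent figure is about 23. At 37 flares the effect is small or nil.
- Study end is not the day of the 28th flare. Data evaluation, the independent analysis, the DSMB review and the sponsor's decision come first (SAP 5.1 and 7.2). This stands, although the lag helps only to the extent that randomisation pauses.
- A reader might infer that the test is invalid or that the rule favours tofacitinib. Neither follows. The expected loss is the same in both arms, so the null test stays valid, the ratio of rates is not biased, and the expected shift is toward no difference. Power hardly moves: at 28 flares without exits and an assumed 50% versus 20%, it is 47% as planned and 51% with the restricted denominator.
- The Protocol Summary lists remission at each visit from Week 24, and SAP 6.2.1.1 presents its binary endpoints by visit through Week 52. So it is too strong to say that the plan defines no time horizon. Reporting by visit does not help a child stopped before Week 24, who is negative at every such visit.

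**Conclusion.** The point holds for a stop at the First Analysis. A child without 24 weeks of possible follow-up is scored as a remission failure, and both rates and their absolute difference are understated in expectation. The affected share is about 9–17% across the exit assumptions, and about 5–11% if the no-exit case is combined with a lag and paused randomisation. At 37 flares it is about 0–6%.

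This rests on the protocol's accrual and exponential hazards, on assumed remission rates, and on remission being unrelated to randomisation date. It is a statement about expected values. With so few late entrants, chance imbalance between arms could move an observed difference either way. The shares count only children who cannot reach remission at all. A child whose inactive disease begins after Day 1 needs longer than 24 weeks.

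The endpoint is secondary, and the primary log-rank test is untouched. The change is still worth making, because under the design's own hazard ratio a boundary crossing at the First Analysis is the most likely outcome.

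**What to change.** In SAP 6.2.1.1 and the clinical remission row of Table 4, make one of two changes.

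1. Compute the remission proportion in both arms among DBFAS children randomised at least 182 days before study end. Day +182 is the upper limit of the DB Week 24 window in SAP Table 6. Randomisation date is fixed before outcome and the cutoff is the same in both arms, so the comparison stays randomised.
2. Report the Aalen-Johansen cumulative incidence of remission, read at the upper limits of the Week 24 and Week 52 windows (Days +182 and +378). Treat flare or other product discontinuation as a competing event and study end as censoring. Reading at exactly Week 24 would miss remissions recorded later in that window.

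The full-DBFAS proportion can stay as a supplementary result. The cost is SAP wording, a short program and a slightly wider confidence interval, because late-randomised children contribute less or nothing.
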